## **Characteristics of the Research Population**

### Number of Subjects

For this study we intend to recruit a total of 3,032 adolescents (1,252 in Aim 1; 1,300 in Aim 2; and 480 in Aim 3—the in-person lab study). Participants will be selected through Dynata, a survey firm. A power analysis was conducted to determine the sample size in which the size of 1,252 participants provides 80% power to detect an effect size of 0.2 SD between conditions.

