**Aim 3-** Statistical considerations: Power and sample size: We based our sample size on the expectation of a racial congruence effect that is small in size for White adolescents (0.2) and larger for Black adolescents (0.3). West our final sample size with the requirement of 80% power to detect the smallest correlation coefficient (at least 0.2) within each group (i.e., 200 Black and 200 White adolescents provide adequate power). Analytic plans: We will follow data cleaning procedures for eyetracking data established by our collaborator [name] for handling data loss or calibration issues.The sampling rate—the proportion of time eyes are directed at the screen—must equal 80% or higher. Participants with <20% sampling rate will be eliminated (typically <5% of participants). Sampling Rates can be low because some rare types of cornea refractions and contact lens types impair the reflection of light the system measures. To account for nonindependence in consumption across blocks, we will conduct analyses using the MIXED procedure in SPSS, and calculate degrees of freedom using a Satterthwaite correction to predict consumption as a function of ad type within blocks 1–4 and separately blocks 5–8. We will include the random intercept of participants, the random intercept of block order, and the random slope of block order to account for linear changes in consumption over time. We will use linear regression to predict calorie intake from visual attention to race-relevant ad features, product, and "likes" for Black and White adolescents

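### The Aim 3 mixed model lists no fixed block-order term, and its random slope cannot by itself capture the average change in intake over blocks

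*Combined protocol and SAP*

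**What the plan says.** In the Data Analysis section, the Aim 3 analytic plan gives the reason for a mixed model: "To account for nonindependence in consumption across blocks, we will conduct analyses using the MIXED procedure in SPSS". The fixed part is to "predict consumption as a function of ad type within blocks 1–4 and separately blocks 5–8". The random part reads: "We will include the random intercept of participants, the random intercept of block order, and the random slope of block order", and the last of these terms is given its purpose in the same sentence: "the random slope of block order to account for linear changes in consumption over time". No fixed effect of block order or time is listed.

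Three other places bear on this:

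- Methods & Procedure, Aim 3, says that each block holds 30 ads, but not which ad types fill which blocks or in what order.
- The same section has hunger rated at baseline and controlled for in analysis. It also makes 150 g of each of four snacks available during the eye-tracking task.
- Study Design calls all three studies randomized controlled trials. Nothing says what is randomised or counterbalanced in Aim 3.

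**The concern.** A random slope and a fixed slope do different jobs. The fixed slope estimates the average change per block; the random slope describes how participants scatter around that average. If only the random slope is fitted, the average change is set to zero. Yet intake from bowls of snacks over successive blocks can be expected to change on average as participants become full, and the plan itself foresees linear change. A baseline hunger rating cannot represent fullness that develops during the session.

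Two consequences are possible. The ignored average trend inflates the estimated slope variance and so widens the standard error for ad type. And if one ad type tends to come earlier, part of the trend can be attributed to ad type.

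**Working it through.** **1. The plan's own figure.** The Aim 3 sample size rests on "80% power to detect the smallest correlation coefficient (at least 0.2) within each group", for which "200 Black and 200 White adolescents provide adequate power". Aim 3 states no alpha; I assume 0.05 two-sided. By Fisher's z, n = ((1.960 + 0.842)/atanh(0.2))² + 3 = (2.802/0.2027)² + 3 ≈ 194 per group, and 200 per group gives 81.2% power. The figure reproduces. It concerns a correlation, so it neither supports nor answers the point about the mixed model. The recruitment target is "480 in Aim 3—the in-person lab study"; the simulation below uses the 400 from the power statement.

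**2. What the listed terms imply.** Take the block-order terms at participant level. For participant i at block position t, with A the ad type:

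y = β0 + β1·A + u_i + v_i·t + e, with v_i having mean 0 and variance τ².

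The modelled mean is β0 + β1·A, which contains no trend. If the true average slope is γ, the slope variance has to absorb it, approximately as τ² + γ². With assumed τ = 8, the apparent slope SD becomes about √(64 + 100) = 12.8 at γ = −10, and √(64 + 400) = 21.5 at γ = −20.

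**3. When bias can arise.** With a participant intercept only, the bias in B minus A is γ × (mean position of B − mean position of A). If every participant shares one order of four blocks and γ = −10:

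- ABAB: −10 × (3 − 2) = −10
- AABB: −10 × (3.5 − 1.5) = −20
- ABBA: −10 × (2.5 − 2.5) = 0

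Simulation of that model returned −10.1, −20.0 and −0.4, as expected.

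**4. Simulation of the candidate models.** Assumed inputs, none of them in the documents: two ad types, four blocks, true ad effect 0, participant SD 40, slope SD 8, residual SD 40 calories, linear average decline of 10 or 20 calories per block. There were 400 participants and 60 runs per row, fitted by REML. Entries are bias / mean standard error, in calories per block.

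| Order | Decline | Random slope, no fixed term | Same, plus crossed random position intercept | Random slope plus fixed linear term |
|---|---|---|---|---|
| Counterbalanced | 10 | 0.1 / 2.12 | 0.2 / 2.06 | 0.2 / 2.06 |
| Counterbalanced | 20 | 0.4 / 2.22 | 0.4 / 2.05 | 0.4 / 2.05 |
| ABAB for all | 10 | −7.7 / 2.07 | −10.1 / 14.2 | −0.1 / 2.23 |
| ABAB for all | 20 | −10.2 / 2.13 | −19.7 / 28.1 | 0.1 / 2.22 |
| AABB for all | 10 | −19.3 / 2.15 | −19.9 / 7.05 | −0.5 / 4.47 |
| AABB for all | 20 | −38.0 / 2.21 | −39.2 / 14.2 | 0.8 / 4.47 |
| ABBA for all | 10 | −0.4 / 2.00 | −0.4 / 15.9 | −0.4 / 2.00 |

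Monte Carlo error on a bias is about 2/√60 ≈ 0.26 (about 0.57 for AABB with the fixed term, where the estimates have SD 4.4). The counterbalanced biases are therefore indistinguishable from zero.

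**5. Reading the table.** With counterbalancing, the standard error ratio without the fixed term is 2.12/2.06 = 1.03 at a decline of 10 and 2.22/2.05 = 1.08 at 20. With a crossed position intercept it is 1.00 in both. Under a shared order the crossed intercept does not rescue the analysis: the bias remains under ABAB and AABB, and the standard error is several times larger.

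**6. A second set of assumed inputs** (228 participants, participant SD 30, slope SD 5, residual SD 40, decline 10) gives the same pattern for the slope-only model. Balanced order: standard error 2.75 against 2.68 with the fixed term, ratio 1.03. A 60/40 order imbalance: bias 1.53 calories. A shared alternating order: bias 8.3 calories.

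**The case against.** The strongest reply has four parts.

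- **The random block-order intercept may do the work.** It is listed alongside the participant intercept, which suggests a second, crossed grouping factor. If so, and if order is counterbalanced, it absorbs average position shifts as well as a fixed term does. This stands. A reader might infer that average satiation is not modelled at all, but the text does not support that: it leaves the meaning of this intercept open.
- **The model sentence is not a full list.** Baseline hunger and awareness of the study's purpose are to be considered in analysis, yet neither appears there. A fixed slope may be intended but unwritten. This is possible, but the sentence does assign the time trend to a specific term, and that term cannot carry it alone.
- **Bias is conditional.** A reader might infer that the ad-type effect will be biased, and take the 8-calorie or larger entries as the expected size. The documents do not support this. They describe no shared order and no imbalance, and they call the study randomized. Association between ad type and position is neither shown nor excluded.
- **Reach is limited.** Aim 3's question about visual attention and calorie intake is answered by a separate linear regression, and the sample size rests on a correlation. Neither is touched here.

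**Conclusion.** The point holds in a limited form. As written, change over blocks is carried by random effects alone, and the random slope cannot estimate an average change. Whether another term covers it depends on two things the plan does not state: whether the block-order intercept is a crossed position factor, and whether ad-type order is counterbalanced.

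With counterbalanced order there is no material bias. The standard error is about 3% to 8% wider at participant level for assumed declines of 10 to 20 calories per block, and about unchanged if position is crossed. If ad type is associated with position, bias is possible; its size depends on the order and on the assumed decline and SDs, so only the direction and the conditions carry over from the simulation.

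Nor would a fixed term remove bias in every case. That result needs a linear trend and an ad type that is not aliased with it.

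**What to change.** 1. Add block position as a fixed effect to both MIXED models (blocks 1–4 and blocks 5–8), keeping the participant random intercept and the random slope of position. Use a linear term by default. Use a categorical term only if ad-type order varies across participants; under one shared order, categorical position is fully aliased with ad type.
2. Define the random intercept of block order: crossed with participants, or within participant.
3. State how ad types are ordered or counterbalanced within blocks 1–4 and 5–8. If each block holds a different ad type in one order shared by all, no position term can separate the two.

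The cost is one degree of freedom per model (three if categorical) and two clarifying sentences, with no extra data. If ad type is correlated with position, the standard error will rise with the fixed term (2.15 to 4.47 in the shared AABB example), because the overlap between ad type and position is then counted as uncertainty.

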### **Purpose of the Study and Background**

### Purpose of the Study

Poor diet and excess weight during adolescence predicts excess weight and diet-related cancers during adulthood, yet there is little research on the risk factors that contribute to weight gain among adolescents. The National Academy of Medicine identifies exposure to food advertisements (ads)as a major predictor of poor diet among children (<12 years of age) because studies have shown that children who are exposed to food ads consume more calories than children who are exposed to nonfood ads. The few food ad studies that have included adolescents (13-17 years of age) found associations between self-reported exposure to television (TV)food ads and poor diet, but we do not know which mechanisms explain this relationship. It is also well established that food companies promote their least healthy products to Black consumers more than White consumers and perceive Black youth as trendsetters. But it is not known whether seeing racially congruent ads (i.e., the person in the ad and the viewer are the same race) places Black adolescents at higher risk of poor diet relative to Whites. Finally, most food ad research is based on TV ads, but food companies are increasingly targeting adolescents on social media. The overall objective of our three studies is to identify the extent to which exposure to Facebook food ads increases the number of calories purchased and consumed by Black and White adolescents. Guided by strong preliminary data, we will test three aims: 1)To evaluate the extent to which exposure to racially congruent vs. incongruent Facebook food ads causes Black vs. White adolescents to purchase more calories for a snack;2)To determine the extent to which exposure to many vs. few "likes" on Facebook food ads causes Black and White adolescents to purchase more calories for a snack; and 3)To test the degree to which visual attention to unhealthy foods, racially congruent people, and/or "likes" in Facebook ads explains the relationship between ad exposure and calorie intake.

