# **Study Design**

The overall objective is to determine the extent to which racially congruent Facebook food ads influence adolescents' food purchases and actual caloric intake. We will accomplish these objectives by conducting three randomized controlled trials (RCTs). The first two aims trials will involve 15minute online surveys in which participants (Black and White adolescents) will rate ads then complete a "food purchasing" task through a virtual vending machine. The third trial will involve an in-person, hour long lab study where participants will be shown ads while investigators covertly monitor their eye movements. The first RCT will answer the research question "Does exposure to racially congruent vs. incongruent Facebook ads for unhealthy foods cause Black (vs. White) adolescents to purchase snacks with more calories?". The second RCT will answer: "Does exposure to many "likes" (vs. few "likes") on Facebook ads for unhealthy foods lead to even higher calorie purchases for both Black and White adolescents?". Lastly, the hour-long study will answer the question: "To what extent does the visual attention to foods vs. people vs. "likes" in ads predict adolescents' caloric intake?" (Aim 3). For the first two online survey trials, we will measure the average calories purchased for a snack and for the last trial we will measure the average calories consumed.

<sup>19 Harris JL, Schwartz MB, LoDolce M, et al. Sugary drink FACTS 2014: Some progress but much room for improvement in marketing to youth. *Rudd Center for Food Policy and Obesity: New Haven, CT*. 2014.

<sup>20 Harris JL, Schwartz MB, Munsell CR, et al. Fast food FACTS 2013: Measuring progress in nutrition and marketing to children and teens. *Yale Rudd Center for Food Policy and Obesity*. 2013.

<sup>21 Grier SA, Kumanyika S. Targeted marketing and public health. Annu Rev Public Health. 2010;31:349-369.

<sup>22 Harris JL, Shehan C, Gross R, et al. *Food Advertising Targeted to Hispanic and Black Youth: Contributing to Health Disparities*. Rudd Center for Food Policy & Obesity; 2015.

<sup>23 Story M, French S. Food Advertising and Marketing Directed at Children and Adolescents in the US. *Int J Behav Nutr Phys Act*. 2004;1(1):3.

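### Aim 3 is worded as showing that attention explains the effect of ads on intake, but the planned analyses test only whether attention predicts intake, and residual appetite can produce that association for product attention

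*Combined protocol and SAP*

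**What the plan says.** The combined protocol and SAP words Aim 3 in two ways. Under Purpose of the Study, the aim is to find how far attention to unhealthy foods, same-race people or likes "explains the relationship between ad exposure and calorie intake". Under Study Design, the question is only to what extent such attention would "predict adolescents' caloric intake".

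The Aim 3 part of Data Analysis plans two separate models:

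- A mixed model will "predict consumption as a function of ad type within blocks" 1–4 and, separately, 5–8. Attention is not listed in it.
- For attention, the plan states: "We will use linear regression to predict calorie intake from visual attention to race-relevant ad features", and adds product and likes as predictors, for Black and White adolescents. No ad-type term, attenuation check or indirect effect is described.

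The sample size is set by "80% power to detect the smallest correlation coefficient (at least 0.2) within each group", with the note that "200 Black and 200 White adolescents provide adequate power". Methods & Procedure (Aim 3) says that one self-rated hunger item will be collected at baseline and controlled for in analyses. The description of the attention regression does not list it.

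**The concern.** To say that attention explains an exposure effect, one must show that ad type changes attention, that attention relates to intake with ad type held fixed, and how much of the ad effect runs through that path. No planned Aim 3 model contains all three variables, and none estimates the effect of ad type on attention. The protocol does use this logic elsewhere: in Aim 1 it keeps the exposure terms, adds affective response, and checks whether the exposure associations shrink. The aim devoted to mechanism has no such step.

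A second problem is separate from the first. Adolescents who are hungrier or more interested in food may both look longer at the product and eat more. If attention is not split into a participant's own average and the deviations around it, this stable difference between people enters the attention coefficient. A positive product-attention result could then arise with no advertising mechanism. If it were reported under the Purpose wording, the conclusion would go beyond the evidence.

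**Working it through.** **1. The plan's own sample size.** Inputs from Data Analysis, Aim 3: r = 0.2, 80% power, 200 per race. Alpha is not stated for Aim 3; I assume two-sided 0.05. By Fisher's z:

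n = ((z_alpha + z_power) / atanh(r))² + 3 = ((1.960 + 0.842) / 0.2027)² + 3 ≈ 194.

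Power at n = 200: Φ(0.2027 × √197 − 1.960) = Φ(0.886) = 81.2%.

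The stated 200 is reproduced. One-sided 0.05 would need 154, and the two-sided 0.017 used in Aims 1 and 2 would need 257, so two-sided 0.05 fits best. The power statement therefore concerns a correlation across participants, not an indirect effect.

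**2. Models set side by side.**

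| Link | Planned model |
|---|---|
| Ad type → intake | Mixed model |
| Ad type → attention | None stated |
| Attention → intake | Linear regression, ad type not listed |
| Ad type and attention → intake, jointly | None stated |

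**3. Residual appetite and product attention.** Assumptions, not figures from the documents: an appetite trait correlates λ with both product attention and intake; attention has no effect on intake; the hunger item captures a share c of appetite variance. The induced correlation is r = λ². After adjustment for hunger, the partial correlation is r(1 − c) / (1 − rc). For r = 0.2:

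- c = 0.25: 0.15 / 0.95 = 0.16
- c = 0.50: 0.10 / 0.90 = 0.11
- c = 0.75: 0.05 / 0.85 = 0.06

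Simulated share of significant attention coefficients (n = 200, two-sided 0.05, 4,000 runs per cell):

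| Hunger item captures | r = 0.1 | r = 0.2 | r = 0.3 |
|---|---|---|---|
| no hunger control | 29% | 82% | 99% |
| 25% | 20% | 61% | 93% |
| 50% | 12% | 34% | 70% |
| 75% | 7% | 13% | 27% |
| 100% | about 5% | about 5% | about 5% |

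**4. Which change removes the artefact.** A second simulation used 200 participants, four blocks (two of each ad type), unit person and block variances, person effects correlated 0.2 or 0.3, no hunger control, and no effect of attention on intake. Across three settings of the ad effects (none; on attention only; on both attention and intake), with 1,500 runs each:

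| Model | 0.2 | 0.3 |
|---|---|---|
| Person-mean regression | 61–63% | 93–94% |
| Raw block attention plus ad type | 57–58% | 90–91% |
| Within-person attention plus ad type | 4–6% | about 5% |

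The first row is below the 82% in step 3 because block noise dilutes the person-mean correlation: 0.2 / (1 + 1/4) = 0.16. Adding ad type alone barely helps. Splitting attention does.

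**The case against.** Several points on the other side stand.

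- The Study Design section asks only about prediction, and the linear regression answers that. A reader might infer that the trial cannot answer Aim 3 at all; the documents do not support this. The conflict is with the Purpose wording.
- A reader might infer that the missing ad-type term is what lets appetite in. Step 4 shows otherwise. The missing term is a gap in the mediation logic; appetite enters through unseparated differences between people.
- The 82% and 99% figures ignore the planned hunger control, so the adjusted rows are the relevant ones. All the loadings and capture shares are assumed.
- The appetite argument applies to product attention. Nothing in the documents suggests that appetite increases looking at people or likes. Total viewing time is held constant, so more looking at food would tend to leave less for other features. The calculation is also for a single predictor, whereas the plan names three.
- The mixed model would reveal it if ad type had no effect on consumption, which partly guards against a false mechanism claim.
- The regression is described in one sentence, without a full covariate list or a statement of whether the data are per participant or per block. Only the sample-size basis is clearly at participant level.

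These limit the point but leave its core. Neither described model connects ad type, attention and intake, so the Purpose conclusion has no analysis behind it.

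**Conclusion.** The concern holds in limited form. As written, the Aim 3 analyses can support a statement that attention is associated with intake, and a separate statement about ad type and consumption. They cannot support the statement that attention explains the ad effect, whatever the p-value of the attention coefficient. This conclusion rests on the text alone.

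The size of the appetite artefact rests on assumptions. At an induced r of 0.2, the same value the design is powered to detect, the false-positive rate for product attention is about 61%, 34% or 13% for hunger capture of 25%, 50% or 75%. Over r = 0.1 to 0.3 the adjusted range is 7% to 93%. The rate returns to about 5% only if the item captures appetite fully or if within-person attention is used. The sample size needed for a mediation analysis cannot be computed, because the documents give no path coefficients or within-person correlations.

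**What to change.** Reconcile Purpose of the Study, Study Design and Data Analysis so that all three state the same Aim 3 question. If the mechanism claim is kept:

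- In the block-level mixed model already planned for consumption, keep ad type and add attention to product, person and likes, each split into a participant-centred term and a person-mean term, with baseline hunger as a covariate.
- Fit a parallel model of attention on ad type.
- Report the indirect effect by race with a participant-level bootstrap interval.
- Use the same per-block consumption measure as the planned mixed model. The described scale holds all four snacks and may not yield calories per snack per block.
- State that attention is not randomised, so the indirect effect still rests on untestable assumptions.

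In either case, state whether the linear regression uses participant-level or block-level data, list its covariates, report it as association only, and limit the 80% power statement at r = 0.2 to it.

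Cost: analysis wording and modest extra programming, using block data the planned mixed model already needs. The downside is an indirect effect that may be less precise than the correlation and has no stated power.

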### **Data Monitoring**

The database will be secured with password protection. The study manager will receive only coded information that is entered into the database under those identification numbers. Electronic communication with outside collaborators will involve only unidentifiable information.

The PI and/or study staff will review all data collection forms on an ongoing basis for data completeness and accuracy as well as protocol compliance.

<sup>34 Granot Y, Balcetis E, Schneider KE, Tyler TR. Justice is not blind: visual attention exaggerates effects of group identification on legal punishment. *J Exp Psychol Gen*. 2014;143(6):2196-2208.

Review of the rate of subject accrual and compliance with inclusion/exclusion criteria will occur monthly during the 4-month recruitment phase and then every 3 months to ensure that a sufficient number of participants are being enrolled and that they meet eligibility criteria and the targeted ethnic diversity goals outlined in the grant proposal.

Data on adherence to the treatment protocol will be collected once and reviewed by research staff, the PI, and the study statistician. Adherence of participants will be evaluated by completing the study. If a participant does not sign the assent form, they will be informed that they cannot participate in the study

This study will be stopped prior to its completion if: (1) the intervention (i.e., exposure to food ads) is associated with adverse effects that call into question the safety of the intervention; (2) difficulty in study recruitment or retention will significantly impact the ability to evaluate the study endpoints; (3) any new information becomes available during the study that necessitates stopping the study; or (4) other situations occur that might warrant stopping the study.

Because our study involves a 15-minute online survey experiment where participants view and rate Facebook food ads, as well as the use of an eye-tracking computer, we do not anticipate the need for an independent monitor nor a study report outline.

